- Post-therapy outcomes: increased O₂ requirement (PaO₂/FiO₂ ratio or SpO₂/FiO₂), supplemental oxygen strategy (e.g. nasal cannula, high-flow nasal cannula, noninvasive ventilation, intubation and invasive mechanical ventilation, rescue ventilation i.e. neuromuscular blocking agents, prone positioning, corticosteroids, ECMO), vasopressors, renal support, ICU LOS, ICU mortality, Hospital LOS, Hospital mortality, 28 day mortality.

Study Agent:

- SARS-CoV-2 convalescent plasma (1 unit, on average ~300 mLs)

Primary Objective/Outcome:

1. Feasibility of performing study pathway consisting of consenting convalescent donors, harvesting convalescent plasma, application for FDA eIND and administering convalescent plasma to the patients
 - a. Feasibility will be defined as 6-7 recipient subjects out of a total proposed number of 10 recipient subjects will complete the study infusion of plasma and be evaluable for follow-up with at least 24 hours' worth of data post transfusion. Post-transfusion data will include assessment of the study process, outcome endpoints and safety endpoints.
2. Type and duration of respiratory support (e.g. CPAP, BiPAP, high-flow nasal cannula, mechanical ventilation)

Primary Endpoint: Number of patients meeting inclusion criteria who received anti-SARS-CoV-2 convalescent plasma in the study period

Secondary endpoints:

1. Cardio-circulatory arrest (at any time)
2. Transfer to ICU
3. ICU mortality and LOS
4. Hospital mortality and LOS
5. Ventilator-free days
6. 28 day mortality

Primary Safety Objective: Evaluate the safety of an investigational treatment with anti-SARS-CoV-2 plasma in hospitalized patients with severe or life-threatening COVID-19

Primary Safety Endpoints:

1. Rapid deterioration of respiratory or clinical status during transfusion of anti-SARS-CoV-2 convalescent plasma
2. Cumulative incidence of serious adverse events during the study period: transfusion reaction (fever, rash), transfusion related acute lung injury (TRALI),

transfusion associated circulatory overload (TACO), transfusion related infection, new acute respiratory distress syndrome (ARDS).

Secondary Objectives:

1. Measure rates, levels and duration of SARS-CoV-2 RNA in nasopharyngeal swabs using RT-PCR among recipients. Other specimen types may be tested as available (e.g., BAL fluid, tracheal secretions, sputum, etc.) or when RT-PCR assays are validated for additional sources (i.e., stool, blood).

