Evaluate the safety of investigational treatment with anti-SARS-CoV-2 plasma in hospitalized patients with severe or life-threatening COVID-19

Secondary Objectives:

Biomarker tests performed in the research lab (e.g. antibody titer, cytokine levels) at days 0, 1, 3, 7 and 14 (additional days 21 and 28 may be included, as available) in the recipient.

Measure rates, levels and duration of SARS-CoV-2 RNA in nasopharyngeal swabs using RT-PCR among recipients. Other specimen types may be tested as available (eg., BAL fluid, tracheal secretions, sputum, etc.) or when RT-PCR assays are validated for additional sources (i.e., stool, blood).

Definitions

- Enrolled: From time consented to participate until designated as a screen failure or have either been discontinued from the study or completed it.
- Screen Failures: signed informed consent, but then determined to be ineligible or withdraws
- Discontinued: withdrawn by investigator or withdraws consent
- Completed: Subjects are considered to have completed when they are followed through day 90 or have had an adverse event or death occurred prior to day 90.

Study population

Plasma Donor Subject Inclusion Criteria for Enrollment

- Age 18 or older
- Able to donate blood per blood bank standard guidelines
- Prior diagnosis of COVID-19 documented by a laboratory test. Patients outside of the UCMC medical system will be asked to provide documentation of COVID-19 positive test.
- Complete resolution of symptoms at least 28 days prior to donation
- Female donors who have never been pregnant, previously pregnant female donors negative for HLA antibodies (HLA screening), or male donors

Plasma Donor Subject Exclusion Criteria for Enrollment

- Unable to give consent
- Unable to donate blood per blood bank standard guidelines
- Unsuccessful blood donation

Plasma Recipient Subject Inclusion Criteria for Enrollment

- Patients must be 18 years of age or older
- Must have laboratory-confirmed COVID-19
- Must have severe or immediately life-threatening COVID-19
 - Severe defined as dyspnea, respiratory frequency \geq 30/min, blood oxygen saturation \leq 93%, partial pressure of arterial oxygen to fraction of inspired oxygen ratio $<$ 300, and/or lung infiltrates $>$ 50% within 24 to 48 hours

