A secure email address at the University of Chicago has been made. . Emails to this address will generate an automatic reply (detailed in the attached recruitment materials). Emails will be viewed by the study staff who will be able to respond if potential participants want to learn more about this research study.

Schedule of Events

Schedule of Events for Plasma Donor Subjects

Table 1. Schedule of events for plasma donor subjects:

| Study period | Screen | Enroll | | Donation |
|--|-----------------|-----------------|--|----------|
| Day | -90 to -28 days | -1 days or more | | 0 |
| Test positive for COVID-19 Patients outside of the UCMC medical system will be asked to provide documentation of COVID-19 positive test | x | | | |
| Subject recruitment and screening | | x | | |
| Consent for participation in donor portion of study | | X | | |
| Donor intake questionnaire via redcap. | | X | | |
| Consent for blood donation using standard UCM Blood Donation processes and procedure | | | | x |
| Donation at UCMC Blood Bank | | | | x |

Table 2: Schedule of Events for Plasma Recipient Subject

| Study period | Screen | Baseline | Transfusion | Follow-up | | | | |
|---|---------|----------|-------------------|-----------|---|---|----|-----------------|
| Day | -7 to 0 | 0 | 0 | 1 | 3 | 7 | 14 | 28 ¹ |
| Eligibility | | | | | | | | |
| Informed consent | x | | | | | | | |
| Demographic and Medical history | x | | | | | | | |
| COVID-19 symptom screen | x | | | | | | | |
| Pregnancy test | x | | | | | | | |
| ABO | x | | | | | | | |
| Application for single patient eIND | x | | | | | | | |
| FDA compassionate use for convalescent plasma | | | | | | | | |
| eIND is approved | x | | | | | | | |
| Study Plasma Administration | | | | | | | | |
| Plasma infusion | | | x | | | | | |
| Study Procedures | | | | | | | | |
| Vital signs | x | x | xxxx ² | x | x | x | x | |
| Physical examination | x | | x | x | | x | | |
| Symptom screen | x | x | x | x | x | x | x | x |
| Concomitant medications | x | x | x | | | | | |
| Assessment with 7-point ordinal scale | | x | | x | x | x | x | x |
| Adverse event monitoring | | x | x | x | x | x | x | x |
| Laboratory testing | | | | | | | | |
| CBC and CMP | | x | | x | x | x | x | |
| Chest x-ray or CT chest if available | x | | | x | x | x | x | |
| SARS-CoV-2 RT-PCR | | x | | x | x | x | x | |
| Blood samples for biomarker tests performed in the research lab | | x | | x | x | x | x | |

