2. Type and duration of respiratory support (e.g. CPAP, BiPAP, high-flow nasal cannula, mechanical ventilation)

Secondary endpoints:

1. Cardio-circulatory arrest (at any time)
2. Transfer to ICU
3. ICU mortality and LOS
4. Hospital mortality and LOS
5. Ventilator-free days
6. 60 day mortality

Primary Safety Endpoints:

1. Rapid deterioration of respiratory or clinical status on transfusion of anti-SARS-CoV-2 convalescent plasma
2. Cumulative incidence of serious adverse events during the study period: transfusion reaction (fever, rash), transfusion related acute lung injury (TRALI), transfusion associated circulatory overload (TACO), transfusion related infection

Secondary Endpoints

1. Rates and duration of SARS-CoV-2 PCR positivity (RT-PCR) at days 0, 3, 7, and 14.

Study procedures for plasma donors

Study procedures for plasma donors who enter the study through the following mechanisms:

- Patients who are on the list of COVID-19 positive patients maintained by the infectious disease team at the University of Chicago Medical Center (UCMC)
- The primary care physician or a treatment team attending of patients who are on the list of COVID-19 positive patients maintained by the infectious disease team at the University of Chicago Medical Center.
- People who are undergoing COVID-19 testing at UCMC.
- Advertisement of this study will take place in community bulletins, throughout the university with posters/fliers, on the internet, UCMC press release and in the local news to ask whether anyone would like to donate blood and participate in this research study.

Day -28 to -90:

- Tested positive for COVID-19. People outside of the UCMC medical system will be asked to provide documentation of COVID-19 positive test.

Day -28 to -90:

- Complete resolution of all COVID-19 symptoms

Day -1 or more:

- Screening for plasma donor inclusion criteria
- Consent for participation in donor portion of study
- Donor questionnaire

Day 0:

- Consent for blood donation using standard UCM Blood Donation processes and procedure
- Blood donation at the UCM Blood Donation Center

Study procedures for investigational plasma recipient

Day -7 to 0:

1. Screening for patient inclusion criteria
2. Subject informed consent (obtained before performing study related activities).

3. Baseline Evaluation (at screening) (much of the information will be obtained from the medical record)
 - Demographics (Age, sex ethnicity, race)

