 - Medical history (timing of exposure to COVID-19 source patient, acute and chronic medical condition, medications, allergies, any drug trial therapy. Any medical condition arising after consent should be recorded as AE)
 - COVID-19 symptom screen (fevers, cough, shortness of breath), day of onset of symptoms
 - Vital signs
 - COVID-19 testing (RT-PCR) from nasopharyngeal, throat, blood or stool (optional) samples. Other clinically-approved SARS-CoV-2 testing may be used if available (e.g. saliva, nares, blood).
 - Blood typing, CBC, comprehensive metabolic panel
 - Urine or serum pregnancy test for females of childbearing potential. Results from laboratory tests obtained up to 7 days before enrollment may be used for the pregnancy test.
 - Stored samples for biomarker tests performed in the research lab (e.g. antibody titer, cytokines)
 - Determination of eligibility as per inclusion/exclusion criteria
4. Application and approval of eIND per FDA guidelines for single patient compassionate use of convalescent plasma

DAY 0:

1. Study Plasma Administration: 1 unit of plasma will be transfused. Time at start and end of infusion will be recorded and Vital signs will be measured immediately prior to infusion, 10-20 minutes after start of infusion, at completion of infusion and 30-60 minutes after the end of the infusion
2. COVID-19 symptom screen (fevers, cough, shortness of breath)
3. Assessment of clinical status (7-point ordinal scale)
4. New medical conditions, concomitant medication, AE evaluation
5. physical examination
6. Blood typing, CBC, comprehensive metabolic panel, C-reactive protein
7. Stored samples for biomarker tests performed in the research lab (e.g. antibody titer, cytokines)

Day 1-7 (or for duration of hospitalization)

1. Vital signs daily
2. COVID-19 symptom screen (fevers, cough, shortness of breath)
3. Assessment of clinical status (7-point ordinal scale)
4. New medical conditions, AE evaluation
5. physical examination
6. CBC, comprehensive metabolic panel, CRP daily
7. COVID-19 testing (RT-PCR) from nasopharyngeal, throat, blood or stool (optional) samples. Other clinically-approved SARS-CoV-2 testing may be used if available (e.g. saliva, nares, blood)

8. Stored samples for biomarker tests performed in the research lab (e.g. antibody titer, cytokines)

Day 28:

Key issues to consider follow up by phone, alive, at home, in hospital (ICU or not), on supplemental O2 or not, back to work, fully, partially, SNF, nursing home, LTAC

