Study data are accessible at all times for the team to review, and to the Independent Safety Monitor upon request. The PIs and co-investigators review study conduct, particularly accrual, drop-outs, and protocol deviations on a quarterly basis. The team reviews adverse events (AEs) individually in real-time and in aggregate on a quarterly basis. The PIs review serious adverse events (SAEs) in real-time. The PIs ensure that all protocol deviations, AEs and SAEs are reported to the IRB according to the applicable regulatory requirements.

1. Safety Evaluations will assess for the safety of anti-SARS-CoV-2 plasma
2. Clinical evaluations: Vital signs and symptom screen on days 0-7, 14 and symptom screens on days 28, 60, and 90.
3. Laboratory evaluations consistent with ongoing medical care may include radiographic imaging modalities such as chest x-rays and chest CT.
4. Safety laboratory tests (ABO typing, pregnancy testing, CBC, CRP, and comprehensive metabolic panel) will be performed at the local CLIA-certified clinical laboratory on days 0-7 and 14.

Event (AE)

Any untoward medical occurrence in a clinical investigation subject who has received a study intervention and that does not necessarily have to have a causal relationship with the study product. An AE can, therefore, be any unfavorable and unintended sign (including an abnormal laboratory finding, for example), symptom, or disease temporally associated with the use of the study product, whether or not considered related to the study product.

Serious Adverse Event (SAE)

An SAE is any adverse event that results in any of the following outcomes:

1. Death
2. Life-threatening (immediate risk of death)
3. Prolongation of existing hospitalization
4. Persistent or significant disability or incapacity
5. Important medical events that may not result in death, be life threatening, or require intervention or escalation of care may be considered a serious adverse event when, based upon appropriate medical judgment, they may jeopardize the subject and may require medical or surgical intervention to prevent one of the outcomes listed in this definition. Examples of such medical events include allergic bronchospasm requiring intensive treatment in an emergency room or at home, blood dyscrasias or convulsions that do not result in inpatient hospitalization.

Unexpected Adverse event: (UAE) An adverse reaction, the nature or severity of which is not consistent with the investigator's brochure.

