Unanticipated Problem (UP)

Unanticipated problems involving risks to subjects or others refer to a problem, event or information item that is not expected, given the nature of the research procedures and the subject population being studied; and which suggests that the research places subjects or others at a greater risk of harm or discomfort related to the research than was previously known. The IRB considers unanticipated problems, in general, to include any incident, experience, or outcome that meets ALL of the following criteria:

1. unexpected (in terms of nature, severity, or frequency) given (a) the research procedures that are described in the protocol-related documents, such as the IRB-approved research protocol, investigator's brochure, drug or device product information, informed consent document, or other research materials; and (b) the characteristics of the subject population being studied, including underlying diseases, behaviors, or traits;
2. related or possibly related to participation in the research (possibly related means there is a reasonable possibility that the incident, experience, or outcome may have been caused by the procedures involved in the research); and

3. suggests that the research places subjects or others at a risk of unknown harm or addition/increased frequency of harms (including physical, psychological, economic, legal, or social harm) than was previously known or recognized.

Unanticipated problems may be adverse events, protocol deviations, noncompliance or other types of problems, but MUST meet all of the criteria listed above. It is the expectation of the IRB that all approved protocol procedures are being followed without alteration unless the IRB has been informed of a protocol change or deviation.

Protocol Deviation: Deviation from the IRB-approved study procedures. Designated serious and non-serious

1. **Serious Protocol Deviation:** Protocol deviation that is also an SAE and/or compromises the safety, welfare or rights of subjects or others
2. **Safety Reporting Requirements**

Reporting Interval

All AEs and SAEs will be documented from the first administration of study product until completion or un-enrollment from the study. All AEs and SAEs will be followed until resolution even if this extends beyond the study-reporting period. Resolution of an adverse event is defined as the return to pre-treatment status or stabilization of the condition with the expectation that it will remain chronic.

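### Adverse event capture has conflicting start points and an end rule that an adverse event can itself trigger, and the SAE and Grade 3+ proportions carry no onset restriction

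*Combined protocol and SAP*

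**What the plan says.** All references are to the combined protocol and SAP.

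**Start of capture**
- Study procedures for investigational plasma recipient, Day -7 to 0, medical history item: "Any medical condition arising after consent should be recorded as AE".
- Safety measures, Reporting Interval: "All AEs and SAEs will be documented from the first administration of study product until completion or un-enrollment from the study".
- Safety measures, AE definition: "Any untoward medical occurrence in a clinical investigation subject who has received a study intervention".
- Table 2: the row "Adverse event monitoring" is blank under Screen (Day -7 to 0). Its first mark is under Baseline, Day 0, in the column before Transfusion.
- Definitions: "Enrolled: From time consented to participate until designated as a screen failure". Enrolment therefore starts at consent.

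**End of capture**
- The Reporting Interval sentence above ends documentation at completion or un-enrolment.
- Definitions, Completed: a subject has completed when "followed through day 90 or have had an adverse event or death occurred prior to day 90".
- The Table 2 footnote and the recipient procedures schedule AE evaluation at Days 28, 60 and 90.

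**What is analysed**
- Analysis of AE data: the share of subjects with an SAE and the share with an AE of Grade 3 or above. No onset window is given. Statistical Analysis sets the denominator at 10.
- Primary safety endpoint 2: "Cumulative incidence of serious adverse events during the study period: transfusion reaction (fever, rash"), followed by further components. The Protocol Summary list ends with "transfusion associated circulatory overload (TACO), transfusion related infection, new acute respiratory distress syndrome (ARDS"). The list in the Endpoints section stops at transfusion related infection and does not name ARDS. No start or end of the study period is defined for an individual subject.

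**The concern.** Recipients enter with severe or life-threatening COVID-19, and consent may precede plasma by up to 7 days while the eIND is applied for and approved. A new condition in that interval is an AE under the medical history wording and is not one under the AE definition or the Reporting Interval. Nothing in the analysis section then separates it from events after plasma. A summary meant to describe what followed the infusion could include events that the infusion cannot have caused.

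The end rule works in the opposite direction. If a minor AE on Day 1 makes a subject complete, and completion ends documentation, a later and more serious event in that subject may not be recorded. The two faults can combine: taken literally, a condition arising after consent could make a subject complete before receiving plasma.

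At stake are the two general safety proportions of a 10-recipient pilot, where one subject is a tenth of the denominator.

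**Working it through.** The plan states no figure on this point, so there is none to reproduce. The check compares the texts and then shows the scale.

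**1. Start rules side by side**

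| Source | Capture starts at | Event on Day -3, consent on Day -5 |
|---|---|---|
| Recipient procedures, Day -7 to 0 | consent | AE |
| Table 2 | Baseline, Day 0 | not monitored |
| AE definition | after receipt of the intervention | not an AE |
| Reporting Interval | first administration | not documented |

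The recipient procedures are the outlier. Table 2 also differs from the last two rows for an event on Day 0 before the infusion. The disputed interval runs from consent to infusion: at most 7 days, and as little as 0 if both fall on Day 0.

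**2. Which safety outputs a pre-plasma event can reach**
- Safety endpoint 1 (deterioration during, or on, transfusion): none.
- Safety endpoint 2 as listed under Endpoints: transfusion reaction, TRALI, TACO and transfusion related infection all presuppose a transfusion, so none of these.
- Safety endpoint 2 as listed in the Protocol Summary: new ARDS can occur before plasma. This is the one named component that could be affected, and only because the study period has no per-subject start.
- Proportions with an SAE and with a Grade 3+ AE: any pre-plasma event that meets the criteria, if it is recorded under the consent rule.

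**3. Scale of one subject**

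With n = 10, one subject is 1/10 = 10 percentage points. For scale, exact (Clopper-Pearson) 95% intervals:
- 0/10 = 0% (0 to 30.8%)
- 1/10 = 10% (0.3 to 44.5%)
- 2/10 = 20% (2.5 to 55.6%)

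**4. Chance that at least one recipient is affected**

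Let q be a recipient's chance of an SAE between consent and plasma. The documents give no value, so every q here is an assumption, and subjects are taken as independent. P(at least one in 10) = 1 - (1 - q)^10:
- q = 0: 0%
- q = 2%: 1 - 0.98^10 = 18%
- q = 5%: 1 - 0.95^10 = 40%
- q = 10%: 1 - 0.90^10 = 65%
- q = 20%: 1 - 0.80^10 = 89%

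**5. End rule followed literally**
- A subject has a mild AE on Day 1 and so meets the completion definition.
- Documentation under the Reporting Interval stops.
- Follow-up to resolution continues, but only for events already recorded.
- After completion, only SAEs suspected to be related to the product are reported.
- A later SAE not suspected to be related, or a later non-serious Grade 3+ AE, is therefore outside the capture rule.
- Each proportion counts subjects, so a loss matters only where the earlier AE did not already place the subject in the numerator. In that case the proportion falls by 10 points.
- The AE evaluations at Days 28, 60 and 90 make no exception for subjects with an earlier AE, so the definition and the schedule conflict.

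**The case against.** The strongest reply is that the consent wording stands alone. The AE definition and the Reporting Interval both tie AEs to receipt of plasma, an SAE is defined as a kind of AE and inherits that limit, and Table 2 has no AE monitoring at screening. The consent sentence sits inside a medical history item and may only be meant to separate history from new conditions. It also does not say whether worsening of the qualifying COVID-19 counts as a condition that has arisen. Condition dates and infusion start and end times are recorded, so with 10 recipients events can be sorted by onset. On the end rule, the visit schedule suggests that staff would keep evaluating AEs through Day 90.

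Most of this stands, and it lowers the likely harm. It does not remove the conflict: site staff have one instruction to record and others not to, and the analysis text does not say that recorded dates will be used to exclude anything. The end rule needs a literal reading to lose data, but that reading is what the definition says.

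Two stronger readings are not supported. A reader might infer that pre-plasma events in general can enter the primary safety endpoint. They cannot: endpoint 1 and every endpoint 2 component in the Endpoints section need a transfusion, which leaves only new ARDS from the Protocol Summary. A reader might also try to size the problem by assuming a daily SAE risk of 2% to 5% over 2 to 7 days, which gives 1 - 0.98^2 = 4.0% to 1 - 0.95^7 = 30.2% of recipients. Neither the risks nor the intervals are in the documents, and consent and infusion may fall on the same day, so the lower end is 0%.

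**Conclusion.** The rules for AE capture conflict at both ends, and this follows from the text without any assumed rate. At the start, one passage captures from consent, Table 2 from Baseline on Day 0, and the AE definition and Reporting Interval from plasma, while the SAE and Grade 3+ proportions have no onset restriction. At the end, an adverse event can count as completion, and completion ends documentation, contrary to the scheduled evaluations.

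The effect is 10 percentage points for each affected subject: upward if the only qualifying event came before plasma, downward if the only qualifying event came later and was not captured. How many subjects would be affected cannot be derived from the documents and may be none; the 18% to 89% above rests wholly on assumed values of q from 2% to 20%. For the primary safety endpoint, the exposure is limited to new ARDS and the undefined study period. This is a descriptive pilot with no hypothesis test, so no error rate or power is at risk. The point should be corrected because the affected proportions are its general safety summaries and the correction is cheap.

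**What to change.** - **Analysis of AE data:** state that both proportions count events with onset at or after the start of infusion through Day 90, whether or not the subject had an earlier AE. Show events between consent and infusion in a separate listing.
- **Table 2, recipient procedures (Day -7 to 0), AE definition and Reporting Interval:** align all four with that window. Direct conditions arising between consent and infusion, including those found at the Day 0 baseline assessment, to the pre-treatment listing.
- **Definitions, Completed:** delete the adverse event alternative, leaving follow-up through Day 90 or earlier death.
- **Primary safety endpoint 2:** define the study period per subject, and reconcile the component lists in the Protocol Summary and the Endpoints section, including whether new ARDS belongs.

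The cost is a few sentences and one listing. No new data collection is needed, because condition dates, infusion times and the Day 28, 60 and 90 evaluations are already planned.
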